6.6 Adaptive Planning

- 6.6.1 Patients will be placed a linear accelerator equipped with an EPID, MLCs and adaptive planning capabilities. All patients will be treated using the SABR, which is planned as explained above in sections 6.1-6.5. Each treatment field will be shaped by the MLCs using an in-house MLC preparation system (3) and transferred through the computer network to the linear accelerator. The daily portal image of each treatment field was aligned off-line to a reference image using a treatment verification tool (6). The reference image will be obtained from the simulation film, which will include the planned treatment isocenter and delineations of each treatment field. Throughout the study, daily setup errors for each treatment field will be delineated separately using the department's adaptive planning software.

6.7 Documentation Requirements

- 6.7.1 Treatment interruptions should be avoided when possible by preventative medical measures and nutritional and psychological counseling. Treatment breaks and reasons need to be clearly documented.

6.8 Compliance Criteria

6.8.1 Section 6 describes appropriate conduct for treatment planning dosimetry. Criteria for both major and minor deviations are provided in Section 6.4. In addition to the criteria in Section 6.4, table 3 in Section 6.5 lists dose volume limits for specific organs and structures. Exceeding these limits by more than 2.5% constitutes a minor protocol violation. Exceeding these limits by more than 5% constitutes a major protocol violation.

6.9 Radiation Toxicity: All acute and late toxicity related to SBRT will be reported. Study accrual will be suspended for and Grade 4 or 5 events possibly related to study treatment.

6.8.1 Toxicities related to Stereotactic Body Radiation Therapy (24): Cough, pneumonitis, atelectasis, bronchial obstruction, bronchial stricture, bronchopleural fistula, chest wall pain, fracture, changes in pulmonary function tests (see below), pulmonary fibrosis, radiation skin changes, including dermatitis from radiation, alopecia, dyspnea, fever, fatigue, pericarditis, pericardial effusion, chest pain – cardiac, palpitations, heart failure, myocardial infarction, paresthesias. All of these toxicities will be graded based on CTCAE 4.0 (Appendix III)

6.8.2 Lung Injury: Radiation pneumonitis is a subacute (weeks to months from treatment) inflammation of the end bronchioles and alveoli. Patients reporting symptoms as above will be promptly evaluated and treated. Mild radiation pneumonitis may be treated with nonsteroidal anti-inflammatory agents or steroid inhalers. More significant pneumonitis will be treated with systemic steroids, bronchodilators, and pulmonary toilet. It is unlikely that symptomatic pneumonitis will occur during the weeks radiation is actually delivered to the patients. However, if a patient experiences pneumonitis before completing therapy, therapy will be put on hold until symptoms resolve. All patients who have pneumonitis will be graded and documented

6.8.3 Bronchial Injury (e.g., bronchial obstruction; bronchial stricture; bronchopleural fistula): Focal collapse of lung secondary to bronchial injury may impair overall pulmonary status. It also makes further assessment of tumor response more difficult as the collapsed lung approximates the treated tumor. Because atelectatic lung and tumor have similar imaging characteristics, radiology reports will often describe the overall process as progressive disease while the actual tumor may be stable or shrinking.

6.8.4 Chest Wall Pain and/or Fracture (Rib): Some patients will experience chest wall pain either as a result of intercostal neuropathy or rib fracture. Focal radiation induced osteoporosis can result in both occult and obvious rib fractures generally propagated by severe coughing/sneezing episodes or chest wall trauma/ The pain typically occurs several months after treatment and may last several more months.

6.8.5 Changes in Pulmonary Function Tests: Patients enrolled to this study may have some degree of impaired pulmonary function as measured by pulmonary function tests (PFTs), including Forced Expiratory Volume in 1 second (FEV1), Forced Vital Capacity (FVC), and Diffusing Capacity for Carbon Monoxide (DLCO). In order to monitor changes in lung function from baseline, a protocol-specific toxicity classification for PFTs has been developed for use with this study. PFTs will be coded for all patients in both treatment groups using this scale. The RTOG Pulmonary Function Test Toxicity Scale is below. PFT acquisition, however, is suggested and not required for this study.

Adverse Event	Grade 1	Grade 2	Grade 3	Grade 4	Grade 5
FEV1 Decline	0.90-0.75 times the patient's baseline value	<0.75-0.50 times the patient's baseline value	<0.50-0.25 times the patient's baseline value	<0.25 times the patient's baseline value	Death
FVC Decline	0.90-0.75 times the patient's baseline value	<0.75-0.50 times the patient's baseline value	<0.50-0.25 times the patient's baseline value	<0.25 times the patient's baseline value	Death

DLCO Decline	0.90-0.75 times the patient's baseline value	<0.75-0.50 times the patient's baseline value	<0.50-0.25 times the patient's baseline value	<0.25 times the patient's baseline value	Death
--------------	--	---	---	--	-------

Table 4: RTOG Pulmonary Toxicity Scale (24)

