Protocol Title: Pilot Study Evaluating Stereotactic Body Radiation Therapy (SBRT) and Adaptive Radiation Therapy (ART) for Pulmonary Metastases from Soft Tissue Sarcomas

NCT Number: NCT01949506

Version Date: February 24, 2017

TITLE

Pilot Study Evaluating Stereotactic Body Radiation Therapy (SBRT) and Adaptive Radiation Therapy (ART) for Pulmonary Metastases from Soft Tissue Sarcomas

Principle Investigator/Radiation Oncology:

[name], MD
[name], MD (Co-PI)

Radiation Oncology Co-Chairs:

[name], MD

Medical Oncology Chair:

[name], MD

Physics Chair

X. [name]

Version Date: **February 24, 2017**

INDEX

Schema

[figure not shown]
Eligibility Checklist

- 1.0 Introduction
- 2.0 Objectives
- 3.0 Patient Selection
- 4.0 Recommended Pretreatment Evaluations
- 5.0 Registration Procedures
- 6.0 Radiation Therapy
- 7.0 Drug Therapy
- 8.0 Surgery
- 9.0 Other Therapy
- 10.0 Tissue/Specimen Submission
- 11.0 Patient Assessments
- 12.0 Data Collection
- 13.0 Statistical Considerations

References

- Appendix I -Performance Status Scoring
- Appendix II -Staging System
- Appendix III -Toxicity Scoring
- Appendix IV -QoL Scoring

TITLE
Pilot Study Evaluating Stereotactic Body Radiation Therapy (SBRT) and Adaptive Radiation Therapy (ART) for Pulmonary Metastases from Soft Tissue Sarcomas
SCHEMA

Patient Population:

Accrual goal is 20 patients with pulmonary metastatic disease from soft tissue sarcoma primaries. A reasonable estimate for accrual at the Medical College of Wisconsin is 5 patients per year and 5 patients per year at Kraemer Cancer Center, West Bend with a conservative estimate of 40 tumors. The estimated duration of the study is 2 years.

Required Sample Size: 20

ELIGIBILITY CHECKLIST

(Y) 1. Does the patient have a pathologically (histologically or cytologically) proven diagnosis of a soft tissue sarcoma?

(Y) 2. Has the patient had a history and physical within 4 weeks of registration?

(Y) 3. Was the patient deemed inoperable by cardiothoracic surgery, declined surgery, or surgery not recommended by the multidisciplinary tumor board?

(Y) 4. Was pre-treatment imaging done within 6-8 weeks prior to registration?

(Y) 5. Is the patient at least 18 years of age?

(Y) 6. Was the Zubrod performance scale 0-2 4 weeks prior to registration?

(Y) 7. Did the patient sign a study-approved informed consent?

(N) 8. Does the patient have >5 pulmonary metastases disease?

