- 4. Ramsey et al. A Technique for Adaptive Image-Guided Helical Tomotherapy For Lung Cancer. *Int. J. Radiation Oncology Biol. Phys.* 2006; 64: 1237–1244.
 - a. Conclusions: Megavoltage CT-based image guidance can be used to position lung cancer patients daily. This has the potential to decrease margins associated with daily setup error. Furthermore, the adaptive therapy technique described in this article can decrease the volume of healthy lung tissue receiving above 20 Gy. However, further study is needed to determine whether adaptive therapy could result in the underdosing of microscopic extension.

2.0

OBJECTIVES

2.1 **Hypothesis and Specific Aims:** The primary objective of the study is to assess acute toxicity of SBRT and adaptive planning for up to 5 pulmonary metastases from STS. We hypothesize that SBRT for pulmonary metastases will result in local control similar to resection with less toxicity.

2.1.1 **Primary Objective:** Assess the acute toxicity of SBRT for \leq 5 pulmonary metastases from soft tissue sarcoma.

2.1.2 **Secondary Objectives:**

- 2.1.2.1.1 Local control
- 2.1.2.1.2 QoL using FACT-L
- 2.1.2.1.3 Late toxicity
- 2.1.2.1.4 Overall Survival

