2	Symptomatic; tube thoracostomy or medical management indicated; limiting instrumental ADL
3	Severe symptoms; limiting self care ADL; endoscopic or operative intervention indicated (e.g., stent or primary closure)
4	Life-threatening consequences; urgent operative intervention with thoracoplasty, chronic open drainage or multiple thoracotomies indicated
5	Death

Bronchial Stricture

Grade	Description
1	Asymptomatic; clinical or diagnostic observations only; intervention not indicated
2	Symptomatic (e.g., rhonchi or wheezing) but without respiratory distress; medical intervention indicated (e.g., steroids, bronchodilators)
3	Shortness of breath with stridor; endoscopic intervention indicated (e.g., laser, stent placement)
4	Life-threatening respiratory or hemodynamic compromise; intubation or urgent intervention indicated
5	Death

Chest-wall Pain

Grade	Description
1	Mild
2	Moderate pain; limiting instrumental ADL
3	Severe pain; limiting self care ADL

Fracture

Grade	Description
1	Asymptomatic; clinical or diagnostic observations only; intervention not indicated
2	Symptomatic but non-displaced; immobilization indicated
3	Severe symptoms; displaced or open wound with bone exposure; disabling; operative intervention indicated
4	Life-threatening consequences; urgent intervention indicated
5	Death

Pulmonary Fibrosis

Grade	Description
1	Mild hypoxemia; radiologic pulmonary fibrosis <25% of lung volume
2	Moderate hypoxemia; evidence of pulmonary hypertension; radiographic pulmonary fibrosis 25 – 50%
3	Severe hypoxemia; evidence of right-sided heart failure; radiographic pulmonary fibrosis

	>50 - 75%
4	Life-threatening consequences (e.g., hemodynamic/pulmonary complications); intubation with ventilatory support indicated; radiographic pulmonary fibrosis >75% with severe honeycombing
5	Death

Radiation Dermatitis

Grade	Description
1	Faint erythema or dry desquamation
2	Moderate to brisk erythema; patchy moist desquamation, mostly confined to skin folds and creases; moderate edema
3	Moist desquamation in areas other than skin folds and creases; bleeding induced by minor trauma or abrasion
4	Life-threatening consequences; skin necrosis or ulceration of full thickness dermis; spontaneous bleeding from involved site; skin graft indicated
5	Death

Dyspnea

Grade	Description
1	Shortness of breath with moderate exertion
2	Shortness of breath with minimal exertion; limiting instrumental ADL
3	Shortness of breath at rest; limiting self care ADL

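### The only study-level safety rule responds to Grade 4 or 5 events; no number of Grade 3 events triggers a review or pause of accrual

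*Combined protocol and SAP*

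**What the plan says.** Section 2.1 states the aim: "The primary objective of the study is to assess acute toxicity of SBRT and adaptive planning". Section 13.1 makes acute and late toxicity the primary endpoint, but gives no acceptable rate, threshold or interim look.

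Section 6.9 has the one rule that acts on the study as a whole: "Study accrual will be suspended for and Grade 4 or 5 events possibly related to study treatment". The words *for and* are most naturally read as *for any*, so that one event is enough. The same section requires all SBRT-related toxicity to be reported.

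A second protective provision, in the lung-injury paragraph under 6.9, applies to one patient at a time: "if a patient experiences pneumonitis before completing therapy, therapy will be put on hold until symptoms resolve". It does not affect accrual, and the paragraph itself considers symptomatic pneumonitis unlikely during the treatment weeks.

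Section 6.8.4 says of chest-wall pain: "Some patients will experience chest wall pain either as a result of intercostal neuropathy or rib fracture". In Appendix III the top of that scale, Grade 3, reads "Severe pain; limiting self care ADL".

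The schema gives the size and pace: "Required Sample Size: 20", and accrual that "is 5 patients per year and 5 patients per year at Kraemer Cancer Center, West Bend".

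**The concern.** In a trial designed to measure toxicity, the monitoring rule should respond to the toxicity that could plausibly accumulate. Here it responds only at Grade 4 or 5. Grade 3 pneumonitis, which Appendix III defines as severe and needing oxygen, does not count, however many patients have it. Some toxicities that the protocol lists for SBRT cannot reach the trigger on the scales it uses.

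What is at stake is a missing response, not missing data. Accrual could run to 20 patients with a high Grade 3 rate, and nothing in the plan would oblige anyone to stop and look at that rate.

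**Working it through.** **Inputs from the documents.** N = 20, from two sites at 5 patients per year each (schema). Trigger: Grade 4 or 5, possibly related (6.9). Toxicity is evaluated at each fraction, at 4-6 weeks, then every 6 months (11.1, 11.2.1). Pneumonitis appears weeks to months after treatment, and chest-wall pain typically several months after (text under 6.9). No Grade 3 or Grade 4-5 rate is given: section 12.2 expects minimal toxicity, and section 1.0 reports very few Grade 3 or 4 complications. **Every event rate below is therefore an assumption.**

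**The plan's own figures.** 20 / (5 + 5 per year) = 2.0 years, which matches "The estimated duration of the study is 2 years". The sample size and the suspension rule have no stated error rate, power or target rate, so there is nothing further to reproduce.

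**Reach of the trigger.** Appendix III has 19 distinct scales. Four end at Grade 3 (cough, chest-wall pain, fatigue, chest pain) and one at Grade 2 (palpitations). These five can never trigger 6.9. Pneumonitis runs to Grade 5, so it can do so if it worsens.

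**Present rule.** With Grade 3 events only, P(suspension) = 0 at every Grade 3 rate. For Grade 4-5 events, P(at least one in 20) = 1 - (1 - p)^20:

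| Grade 4-5 rate | P(at least one) |
|---|---|
| 1% | 18% |
| 2% | 33% |
| 5% | 64% |
| 10% | 88% |

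Grade 3 rates of 10%, 20%, 30% and 40% give 2, 4, 6 and 8 expected patients of 20. The chance of at least 4 affected is 13%, 59%, 89% and 98%. With 30% Grade 3 and 2% Grade 4-5, the chance of no Grade 4-5 event is 0.98^20 = 67%, and the chance of none together with at least 4 Grade 3 patients is 60%. With 30% and 1% these are 82% and 73%.

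**Illustrative boundary.** Pause for review at 3 or more of 5, 3 or more of 10, or 4 or more of 15 patients with Grade 3 or higher. Three of the first 5 implies at least 3 of the first 10, so over all looks

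B(p) = P(X10 >= 3) + P(X10 <= 2 and X15 >= 4),

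where X10 and X15 are the affected patients among the first 10 and 15.

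| Visible rate p | Sum | B(p) |
|---|---|---|
| 10% | 0.070 + 0.019 | 9% |
| 15% | 0.180 + 0.055 | 23% (0.23495 unrounded) |
| 20% | 0.322 + 0.096 | 42% |
| 30% | 0.617 + 0.131 | 75% |

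**Late onset.** If only half of the Grade 3 or higher events are visible at the look, a true 20% acts as 10% and a true 30% as 15%. The pause probabilities fall from 42% to 9% and from 75% to 23%. Accrual also continues meanwhile: at 10 patients per year, about 5 enrol in one 6-month gap between visits.

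**Both rules together.** Let p4 be the Grade 4-5 rate and p3 = 0.10 - p4 the Grade 3 rate. Then

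P(any pause) = 1 - (1 - p4)^20 x [1 - B(p3 / (1 - p4))].

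- p4 = 1%: 1 - 0.818 x (1 - 0.070) = 24%, against 18% from the present rule alone.
- p4 = 2%: 1 - 0.668 x (1 - 0.053) = 37%, against 33% alone.

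**The case against.** The strongest reply is that a pause for any possibly related Grade 4 or 5 event is already conservative for a 20-patient pilot with low expected toxicity, and that no figure in the documents shows the choice to be wrong. That stands in part. The present rule is defensible for what it covers, and the proposal keeps it. But a low expectation is what monitoring is there to test, and if it is right the added boundary will seldom act.

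A reader might infer that Grade 3 toxicity would go unseen until the final tabulation. The documents do not support that: toxicity is evaluated at every fraction and every follow-up visit, and all of it is reported. What is missing is a required response to the count.

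A reader might also infer that Grade 3 is the level SBRT is most likely to produce. Section 1.0 points the other way: it reports very few Grade 3 or 4 complications, and no pulmonary toxicity of Grade 3 or higher in the retrospective sarcoma series. Section 6.8.4 expects chest-wall pain but gives no grade. The 30% rate used above is a stress case, not a forecast.

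The scale ceilings are not a drafting fault. Those scales simply end there, and serious related events such as fracture, dyspnea and decline in lung function have scales that reach Grade 5. The ceilings matter only because the one rule starts above them.

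Finally, looks tied to the 4-6 week visit would miss much late pneumonitis and chest-wall pain. This stands fully, and the fix has to allow for it.

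Monitoring could exist outside these documents, but they mention none and the index lists no such section. If it exists and covers Grade 3 events, a cross-reference would answer the point.

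**Conclusion.** The concern holds. Section 6.9 is the only study-level safety rule; the pneumonitis hold is for an individual patient. No number of Grade 3 events pauses accrual or prompts a review, and five of the 19 Appendix III scales cannot reach the trigger. These statements follow from the text and need no assumed rate.

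The size does depend on assumed rates. With 30% Grade 3 and 1% to 2% Grade 4-5, the chance of reaching 20 patients with at least 4 Grade 3 cases and no trigger is 60% to 73%. The calculations treat patients as independent and, except in the late-onset check, events as visible at once. The single-event reading of 6.9 rests on taking *for and* as *for any*.

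This should be changed, because the gain is specific and the cost small. It does not show that the trial is unsafe or that Grade 3 toxicity would be overlooked.

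**What to change.** Amend section 6.9 as follows.

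1. Correct *for and*, and keep the Grade 4-5 trigger.
2. Add a pause-for-review boundary for possibly related Grade 3 or higher toxicity, counted per patient, at an acceptable rate that the sponsor sets. The 3/5, 3/10, 4/15 boundary is only an illustration.
3. At each look, for example when patients 5, 10 and 15 have had the 4-6 week visit, count all such events to date in all treated patients, including those first seen at or between the 6-monthly visits. Repeat the count as later events are reported.
4. State the operating characteristics for the rate visible at the look, and jointly with the Grade 4-5 trigger. The figures above cover three fixed looks in exactly 5, 10 and 15 patients. Repeat counts, and counts that include further treated patients, will raise the pause probability, so the final rule needs its own calculation.
5. Say who reviews a pause and what the review must show to reopen or close accrual.

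Cost: a short amendment with no added visits, since the grades are already collected. The downside is some extra pauses at an acceptable rate: with 10% Grade 3 or higher, the chance of any pause rises by about 6 percentage points if 1% is Grade 4-5 (18% to 24%), or about 4 if 2% is (33% to 37%). Most of that total comes from the existing trigger.

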7.0 DRUG THERAPY

NOT APPLICABLE TO THIS STUDY

8.0 SURGERY

NOT APPLICABLE TO THIS STUDY

9.0 OTHER THERAPY

9.1 Supportive Therapy

9.1.1 All supportive therapy for optimal medical care will be given during the study period at the discretion of the attending physician(s).

10.0 TISSUE/SPECIMEN SUBMISSION

NOT APPLICABLE TO THIS STUDY

11.0 PATIENT ASSESSMENTS

11.1 Study Parameters

Assessments	Pre-Study Entry	During Therapy (each fraction)	At 4-6 Weeks (+/- 1 month) after SBRT	Every -6 months (+/- 1 month) after RT for 12years
History/physical,	X		X	X
Zubrod PS	X	X	X	X
Toxicity Evaluation		X	X	X
QoL (FACT-L)	X			X
CT of the Chest	X*			X
PET/CT	X**			If Needed***
PFTs	X (not required)			X** (not required)

PFTs are not required for this protocol. PFTs may be done pre-treatment and 3 months after therapy and as clinically indicated.

*CT scan- within 6-8 weeks of study entry

** PET/CT -may be omitted if not covered by insurance although is recommended to assist in treatment planning and to assess the appropriateness of study therapy.

***PET/CT-to be done at discretion of physician

11.2 PATIENT ASSESSMENTS

11.2.1 Patients will be seen 4 to 6 weeks after the last fraction of radiation therapy, every 6 months for 2 years.

11.2.2 Prior to each visit, a CT of the chest with contrast will be obtained for disease assessment. If there is deemed to be progressive disease, a PET scan will be obtained per discretion of the physician. Biopsy is recommended although will be at the discretion of treating physician. Treatment after failure will be at the treating teams discretion and documented.

11.2.3 QOL assessments will be made using the FACT-L questionnaire. Questionnaires will be given every 6 months for 2 years.

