3.2 Conditions for Patient Ineligibility

- 3.2.1 Patients who have uncontrolled extra-pulmonary disease
- 3.2.2 Pregnant women
- 3.2.3 Patients who have greater than 5 pulmonary lesions at the time of study enrollment
- 3.2.4 Patients who have disease progression outside the lungs within 3 months of enrollment on the study.
- 3.2.5 Disease pathology other than sarcoma subtypes
- 3.2.6 Patients with a history of metastatic disease from a primary other than sarcoma

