4.0 RECOMMENDED PRETREATMENT EVALUATIONS

- 4.1 CT of the chest **within 6-8 weeks** of study entry
- 4.2 Documentation of extra-thoracic disease control within 6 weeks of study entry
- 4.3 PFTs are recommended, but not required within 3 months study entry

5.0 REGISTRATION PROCEDURES: Eligible patients will be registered per the CTO standard procedure.

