12. DATA COLLECTION

12.1. Study Design:

This is a non-randomized Phase II pilot protocol to determine the feasibility, toxicity, and disease control (overall and progression-free survival) using SBRT in patients with pulmonary oligometastatic disease from soft tissue sarcoma primaries.

12.2. Primary Endpoint:

The primary aim of this study is to assess toxicity and quality of life from SBRT. All patients will be followed for the primary endpoint for a minimum of 3 years. Based on historical data, we expect there will be minimal toxicity, both acute and long term. Adverse event rates will be compared at specific time points (3, 6 and 12 months after completion of SBRT). Quality of life will be measured with the FACT-L questionnaire (Appendix IV).

12.3. Secondary Endpoint:

The secondary objective of this study is to assess local and regional control, progression-free survival and overall survival. Local and regional recurrence will be defined for each lesion per criteria in section 11.3.2. Disease-free survival is defined as the time from randomization until documented disease-recurrence or death, whichever occurs first. Patients who are disease-free and alive at the time of analysis will be censored at the time of their last follow-up. Patients will be followed for disease-free survival for a minimum of 3 years.

12.4. Endpoint Analysis:

Crude rates of locoregional recurrences will be documented as well as the time to development of recurrence or relapse. Time of last follow-up or death will also be noted. This will allow us to calculate progression free and overall survival rates.

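### Section 12 reports progression-free and disease-free survival at any site, but follow-up schedules imaging of the chest only, so asymptomatic extra-thoracic progression may be missed or dated late

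*Combined protocol and SAP*

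**What the plan says.** Section 12.3 states: "The secondary objective of this study is to assess local and regional control, progression-free survival and overall survival". Sections 12.1 and 12.4 also list PFS among the results. PFS has no definition of its own. DFS is defined as the "time from randomization until documented disease-recurrence or death, whichever occurs first", with no restriction by site, and 12.3 adds: "Patients who are disease-free and alive at the time of analysis will be censored at the time of their last follow-up".

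For follow-up, 11.2.2 says: "Prior to each visit, a CT of the chest with contrast will be obtained for disease assessment". The table in 11.1 agrees that chest CT is the only unconditional follow-up imaging. PET/CT is marked as needed, at the physician's discretion. In 11.2.2 it comes up only as a response to progression: "If there is deemed to be progressive disease, a PET scan will be obtained per discretion of the physician". History and physical examination are scheduled at every follow-up visit.

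At entry, Section 4.2 asks for "Documentation of extra-thoracic disease control within 6 weeks of study entry", without naming a modality. Section 3.2.1 excludes "Patients who have uncontrolled extra-pulmonary disease", while 3.1.3 and 3.2.4 also rule out extra-pulmonary progression in the 3 months before enrolment. Patients with controlled extra-pulmonary disease can therefore enter.

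**The concern.** The endpoint and the search for its events do not match. Lung progression is looked for by CT every 6 months. Progression elsewhere has no scheduled imaging and no criterion, and the entry check in 4.2 has no follow-up counterpart beyond history and examination.

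Censoring adds to this. A patient recorded as disease-free is censored at last follow-up, not at the last assessment able to show disease at every site. Extra-thoracic time that nobody observed then counts as event-free.

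Under-detection and late dating act in one direction: observed PFS and DFS rise, and the mix of recorded first events shifts toward the lung. A reader of the results would take plain PFS to cover the whole body.

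**Working it through.** **The plan's own figure.** The sample size follows from accrual: (5 + 5) patients per year × 2 years = 20. There is no power calculation and no planned test of PFS or DFS, so nothing else can be reproduced.

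**Coverage of each part of the plan**

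| Element | Where | Sites covered |
|---|---|---|
| PFS; DFS to any documented recurrence or death | 12.1, 12.3, 12.4 | Any site |
| Documentation of disease control at entry | 4.2 | Extra-thoracic |
| Scheduled follow-up imaging | 11.1, 11.2.2 | Chest |
| Discretionary PET/CT | 11.1, 11.2.2 | Not scheduled |
| History and physical | 11.1 | Any site, if symptomatic or palpable |
| Progression criteria | 11.3.2 | Treated lesion, its margin, involved lobe, uninvolved lobes |

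Only history and physical links the schedule to extra-thoracic events. Asymptomatic, isolated extra-thoracic progression is the part at risk.

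**Size per patient.** 1/20 = 5 percentage points of a landmark proportion. This applies only to a patient who is undetected, has no lung progression and is alive at the landmark, because death is itself an event.

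**Illustration at 2 years.** Assumptions not found in the documents: 14 of 20 patients progress within 2 years; 10–40% of them progress first outside the chest; none of these is detected or progresses in the lung by 2 years. From the Introduction (Section 1.0): 2-year survival of 32–87% after SBRT for lung metastases from various primaries, assumed to apply to these patients.

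- Patients affected: 14 × 0.10 = 1.4 to 14 × 0.40 = 5.6.
- Ignoring death: 1.4/20 = 7 points to 5.6/20 = 28 points.
- Alive at 2 years: 1.4 × 0.32 = 0.45 to 5.6 × 0.87 = 4.87.
- Overstatement: 0.45/20 = 2 points to 4.87/20 = 24 points.

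**Illustration of late dating, at 12 months.** All inputs are assumed: exponential time to progression T with median m = 6 or 12 months; a share s = 10–50% of first progressions outside the lung only; an exponential lag to symptoms with mean L = 6 or 12 months; visits every 6 months. Let a = ln 2/m and b = 1/L. Then

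observed PFS at 12 months = (1 − s)·e^(−12a) + s·P, with P = (b·e^(−12a) − a·e^(−12b))/(b − a).

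- Smallest effect (m = 12, L = 6, s = 0.1): P = 0.693, so 0.9 × 0.50 + 0.1 × 0.693 = 0.519 against a true 0.50, about 2 points.
- Largest effect (m = 6, L = 12, s = 0.5): P = 0.673, so 0.5 × 0.25 + 0.5 × 0.673 = 0.462 against a true 0.25, about 21 points.

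A simulation of 400,000 draws on the same assumptions agrees. It gives a mean dating delay of about 3.2–3.3 months if all sites are imaged every 6 months, and about 9–15 months for progressions found only through symptoms. Neither calculation includes death or later lung progression, both of which would shrink the effect.

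**The case against.** The strongest reply is that little rests on these endpoints. PFS and DFS are absent from the objectives in 2.1.2 and from the wording of 13.2, although 13.2 refers to Section 12. They carry no test, threshold or decision rule. The stated hypothesis in 2.1 concerns local control and toxicity. This stands, and it keeps the point to a matter of labelling and ascertainment.

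Second, the plan has other routes to detection. History and physical is done at each visit, the 11.1 table allows PET/CT without requiring prior progression, and the PET trigger in 11.2.2 is not confined to lung progression. Sections 3.1.3 and 3.2.4 also screen out recent extra-pulmonary progressors. This stands too. A reader might infer that extra-thoracic progression will be missed as a matter of course; the documents support only that asymptomatic disease may be.

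Third, some undetected progressions end in death, which 12.3 counts. That is why the 7–28 point range, which ignores death, should not be used as the size.

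Fourth, one could say that chest imaging is enough because the lung is the question. That is reasonable, but it is an argument for calling the endpoint intrathoracic, which Section 12 does not do.

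**Conclusion.** The mismatch is real and worth correcting. Section 12 claims disease control at any site, while the schedule and the criteria observe the chest. The direction of bias is upward for PFS and DFS.

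The size cannot be fixed from the documents. About 2–24 points at 2 years is an illustration. It rests on an assumed 14 of 20 progressing, an assumed 10–40% doing so first outside the chest, no detection or lung progression, and borrowed survival figures from mixed primaries. Any detection or later lung progression lowers it.

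Three stronger readings are not supported. The trial's main results are not undermined: toxicity, local control and overall survival do not depend on extra-thoracic imaging. No comparison with historical PFS is invalidated, because the protocol plans none. Nor does it follow that any-site PFS or DFS must be dropped; it can be reported if its limits are stated.

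A related gap needs separate reconciliation: "Patients will be followed for disease-free survival for a minimum of 3 years", whereas the visits in 11.2.1 run for 2 years.

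**What to change.** In 12.1, 12.3 and 12.4, make the endpoint that the schedule supports intrathoracic progression-free survival, and specify:

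- **Start:** first SBRT fraction. The DFS definition starts at randomization, but 12.1 describes a non-randomized study.
- **Event:** intrathoracic progression on any chest imaging, scheduled or not, or death. Tie the criteria to 11.3.2, stating which categories count (including uninvolved lobes) and how growth is classed when the PET or biopsy confirmation that 11.3.2 asks for was not done, since 11.2.2 leaves both to discretion.
- **Censoring:** at the last chest imaging, not at last follow-up.
- **Extra-thoracic progression:** not an event and not a reason to censor. Record it separately with its date and mode of detection (symptoms, examination, discretionary PET or other imaging).

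If any-site PFS or DFS is still reported, make it supportive and state that extra-thoracic events were only clinically detected.

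The alternative is to schedule extra-thoracic assessment with matching criteria. That would keep the any-site endpoint, but adds assessments for 20 patients in support of a descriptive outcome.

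Cost of the recommended change: Section 12 wording, a link to 11.3.2 and one CRF item. It needs no added scans, visits or patients. The downside is a narrower disease-control claim.
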